9.2.2. Reactogenicity

Reactogenicity events are solicited events which are common and considered as possible to occur following administration of this type of vaccine. Reactogenicity (solicited) events are recorded only for 8 days post vaccination (day of the vaccination inclusive). Solicited events (reactogenicity events) which match at least one of the below criteria must be also recorded as AE/SAE or unsolicited AE/SAE:

- symptom/event continues/occurs beyond 7 days post vaccination day (unsolicited AE/SAE)
- reactogenicity symptom/event(s) required medical (i.e. physician's) assistance (AE/SAE)
- reactogenicity symptom/event has been graded by subject or by investigator as severe (AE/SAE)
- oral body temperature of severe grade as per section 9.2.2 Table 8 (AE/SAE)

Per PI/SI's judgment, also cases of symptoms/events occurring within 8 days post vaccination (day of the vaccination inclusive) not meeting the above criteria can be recorded as SAE.

The following Toxicity Grading Scales will be used by PI/SI to grade solicited injection site and systemic (subjective and quantitative) reactions in order to assess whether they qualify as AE/SAE, and if they are severe enough to delay administration of second dose:

Table 5: Injection Site Reactogenicity Grading

Injection Site Reaction	Mild (Grade 1)	Moderate (Grade 2)	Severe (Grade 3)
Pain – experienced without touching the injection site (spontaneous discomfort)	Subject is aware of pain, but it does not interfere with daily activity, and no pain medication is taken	Subject is aware of pain; there is interference with daily activity or it requires repeated use of a non-	Subject is aware of pain, and it prevents daily activity or requires any use of a narcotic pain reliever

Injection Site Reaction	Mild (Grade 1)	Moderate (Grade 2)	Severe (Grade 3)
		narcotic pain reliever for >24 hours	
Tenderness – hurts only when injection site is touched or the arm is moved	The area immediately surrounding the injection site hurts only when touched or with arm motion, and it does not interfere with daily activity	The area immediately surrounding the injection site hurts when touched or with arm motion, and it interferes with daily activity	The area immediately surrounding the injection site hurts when touched or with arm motion, and it prevents daily activity
Pruritus (Itching)	Does not interfere with daily activity	Interferes with daily activity	Prevents daily activity
Ecchymosis (Bruising)*	Does not interfere with daily activity	Interferes with daily activity	Prevents daily activity
Erythema (Redness)*	Does not interfere with daily activity	Interferes with daily activity	Prevents daily activity
Induration (Hardness)/Swelling*	Does not interfere with daily activity	Interferes with daily activity	Prevents daily activity

* Will be also measured in mm but size will not be used as criterion for stopping the trial

Ecchymosis, erythema, and induration /swelling as analyzed by measurement will be graded as follows:

Table 6: Injection Site Reactogenicity Measurements

Injection Site Reaction	Small	Medium	Large
Ecchymosis *	<20 mm	20 mm – 50 mm	>50 mm
Erythema*	<20 mm	20 mm – 50 mm	>50 mm
Induration /Swelling*	<20 mm	20 mm – 50 mm	>50 mm

* Will not be used as criterion for stopping the trial.

Table 7: Subjective Systemic Reactogenicity Grading

Systemic (Subjective)	Mild (Grade 1)	Moderate (Grade 2)	Severe (Grade 3)
Feverishness (Chills/Shivering/Sweating)	No interference with daily activity	Nonsignificant interference with daily activity	Significant interference, prevents daily activity
Fatigue (Tiredness)	No interference with daily activity	Nonsignificant interference with daily activity	Significant interference, prevents daily activity
Malaise (General Unwell Feeling)	No interference with daily activity	Nonsignificant interference with daily activity	Significant interference, prevents daily activity

Systemic (Subjective)	Mild (Grade 1)	Moderate (Grade 2)	Severe (Grade 3)
Myalgia (Body Aches/Muscular Pain)*	No interference with daily activity	Nonsignificant interference with daily activity	Significant interference, prevents daily activity
Arthralgia (Joint Pain)*	No interference with daily activity	Nonsignificant interference with daily activity	Significant interference, prevents daily activity
Headache	No interference with daily activity	Nonsignificant interference with daily activity	Significant interference, prevents daily activity
Nausea	No interference with daily activity	Nonsignificant interference with daily activity	Significant interference, prevents daily activity

* Not at injection site.

Oral temperature[#] will be graded as follows:

Table 8: Quantitative Systemic Reactogenicity Grading^{20,21}

Systemic (Quantitative)	Mild (Grade 1)	Moderate (Grade 2)	Severe (Grade 3)
(Age <60) Fever* - oral [†]	38.0°C – 38.4°C	38.5°C – 38.9°C	>38.9°C
(Age 60+) Fever* - oral [†]	37.3°C – 37.7°C	37.8°C – 38.2°C	>38.2°C

[#] Oral temperature assessed on Day 0 prior to the first primary series study vaccination will be considered as baseline.

* A fever can be considered not related to the study product if an alternative etiology can be documented.

[†] Subjects must not eat or drink anything hot or cold, or smoke within 10 minutes prior to taking oral temperature.

9.2.3. Additional Adverse Event Severity Grading

Pulse and Blood pressure changes will be graded according to the PI/SI judgment taking into consideration subject's medical history, concomitant medications, and baseline values.

9.2.4. Serious Adverse Events

An AE or suspected AE is considered “serious” if, in the view of either the investigator or sponsor, it results in any of the following outcomes/meets any of the following:

- death,
- a life-threatening AE*,
- inpatient hospitalization or prolongation of existing hospitalization (excluding pre-planned elective surgeries or other pre-planned hospitalizations; for this option it is not required that they were pre-planned solely before Visit 1, they might be pre-planned also after Visit 1),
- a persistent or significant incapacity or substantial disruption of the ability to conduct normal life functions,
- a congenital anomaly/birth defect

- an important medical events that may not result in death, be life-threatening, or require hospitalizations may be considered serious when, based upon appropriate medical judgment they may jeopardize the patient or subject and may require medical or surgical intervention to prevent one of the outcomes listed in this definition. Examples of such medical events include allergic bronchospasm requiring intensive treatment in an emergency room or at home, blood dyscrasias or convulsions that do not result in inpatient hospitalization, or the development of drug dependency or drug abuse.
- Note: all AESIs will also be considered SAEs as within the confines of this protocol are deemed as important medical events
- Note: cases of NOCIs which meet criteria of SAE will be recorded as SAE with annotation that they are also considered NOCIs.
- Note: ILI cases meeting seriousness criterion/criteria should be recorded as SAE in parallel with recording them as ILI cases, except for periods of 8 days post vaccination day (day of the vaccination inclusive) for both vaccine doses when such cases will only be recorded as SAE.

* Life-threatening AE. An AE is considered “life-threatening” if, in the view of either the investigator or sponsor, its occurrence places the patient or subject at immediate risk of death. It does not include an AE that, had it occurred in a more severe form, might have caused death.

All SAEs will be:

- Assessed for severity and relationship to study product and alternate etiology (if not related to study product) by a licensed study physician.
- Recorded on the appropriate paper SAE form and in eCRF.
- Followed through resolution by a licensed study physician.
- Reviewed and evaluated by the DSMB (periodic review unless related)

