3.2. Study Outcome Measures

3.2.1. Primary Outcome Measures

Safety

- Occurrence of vaccine-related SAEs from the time of the first study vaccination (M-001 or placebo) until end of first passive surveillance period
- Occurrence of NOCIs from the time of the first study vaccination (M-001 or placebo) until end of first passive surveillance period
- Occurrence of solicited injection site and systemic reactogenicity events on the day of each study vaccination through 8 days after each study vaccination (day of the vaccination inclusive)
- Occurrence of unsolicited AEs from the time of first study vaccination through 22 days after each study vaccination (day of the vaccination inclusive)
- Occurrence of all SAEs, regardless of the assessment of relatedness, from the time of receiving the first M-001 study vaccination until end of first passive surveillance period

Clinical Efficacy

- Percentage of either qRT-PCR or culture-confirmed influenza cases in the M-001 experimental group vs. placebo (during period of ≥ 15 days after the second vaccination until epidemiological levels of influenza are low as defined by the medical director) caused by any influenza A or B virus in association with a protocol defined Influenza Like Illness (ILI is defined as symptoms that include one of the respiratory symptoms (sore throat, cough, sputum production, nasal discharge or congestion, wheezing or difficult breathing) and at least one additional systemic symptom [fever (oral temperature $>37.2^{\circ}\text{C}$ for age 50-59, or $>36.7^{\circ}\text{C}$ for age 60 or more, or increased $\geq 1.3^{\circ}\text{C}$ from baseline), headache, myalgia and/or arthralgia, chills, and fatigue (tiredness for at least 12 hours)]. NP or combined nasal and throat swab will be collected from participants who meet the ILI definition within 24 hours from ILI being reported to or identified by study personnel for qRT-PCR analysis of influenza A and/or B virus. PCR confirmed samples will be further analyzed for culture confirmation.

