9.2. Safety Assessment

9.2.1. Adverse Events

Adverse Event (AE): International Conference on Harmonisation (ICH) E6 defines an AE as any untoward medical occurrence in a patient or clinical investigation subject administered a pharmaceutical product regardless of its causal relationship to the study treatment. An AE can therefore be any unfavorable and unintended sign, symptom, or disease temporally associated with the use of a medicinal (investigational) product. The occurrence of an AE may come to the attention of study personnel during study visits and interviews of a study recipient presenting for medical care, or upon review by a study monitor.

AEs, will be captured on the appropriate data collection form and electronic case report form (eCRF) as described below in terms of reporting periods. Information to be collected for AEs includes event description, date of onset, licensed study physician's assessment of severity and relationship to study product and considered etiology (if case not related or unlikely related to study product) date of resolution of the event, seriousness and outcome. AEs while on study will be documented appropriately regardless of relationship. AEs will be followed to resolution.

Any medical condition that is present at the time that the subject is screened will be considered as baseline and not reported as an AE. However, if the severity of any pre-existing medical condition increases, it may be recorded as an AE or SAE.

AEs must be graded for severity and assessed for relationship to study product (see definitions below). AEs characterized as intermittent require documentation in the subject's file of onset and duration of each episode. It is up to PI's decision whether the episodes are recorded in the eCRF as separate events or under one event with comment added on the intermittent (or similar) nature of the event. The start and stop date of each reported AE will be recorded on the appropriate data collection form and eCRF within study periods as described below.

•Unsolicited AEs – which do not meet SAE criteria, nor ILI, AESI or NOCI definition should be reported only until ~22 days post each study vaccination, thus - per protocol – such AEs, if they occurred later than 22 days post study vaccination day, should not be recorded in the AE section of the eCRF. They still need to be documented in the subject's study file at the site.

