## 4. SAFETY ENDPOINTS

### 4.1 Safety Definitions

The following definitions are taken from the International Conference on Harmonisation (ICH) E6 Guideline.

**Adverse Event (AE):** An AE as any untoward medical occurrence in a patient or clinical investigation subject administered with a pharmaceutical product regardless of its causal relationship to the study vaccine. An AE can therefore be any unfavourable and unintended sign, symptom, or disease temporally associated with the use of a medicinal (investigational) product.

Any medical condition that is present at the time that the subject is screened will be considered as baseline and not reported as an AE. However, if the severity of any pre-existing medical condition increases, it may be recorded as an AE.

The severity or intensity of AE was noted as mild, moderate, or severe.

**Serious Adverse Event (SAE):** An AE or suspected AE is considered “serious” if, in the view of either the investigator or sponsor, it results in any of the following outcomes/meets any of the following:

- death,
- a life-threatening AE,
- inpatient hospitalization or prolongation of existing hospitalization (excluding pre-planned elective surgeries or other pre-planned hospitalizations),
- a persistent or significant incapacity or substantial disruption of the ability to conduct normal life functions,
- a congenital anomaly/birth defect,
- an important medical event that may not result in death, be life-threatening, or require hospitalizations may be considered serious when, based upon appropriate medical judgment they may jeopardize the patient or subject and may require medical or surgical intervention to prevent one of the outcomes listed in this definition. Examples of such medical events include allergic bronchospasm requiring intensive treatment in an

---

 Life-threatening AE. An AE is considered “life-threatening” if, in the view of either the investigator or sponsor, its occurrence places the patient or subject at immediate risk of death. It does not include an AE that, had it occurred in a more severe form, might have caused death.

emergency room or at home, blood dyscrasias or convulsions that do not result in inpatient hospitalization, or the development of drug dependency or drug abuse.

The definitions below are used by BiondVax:

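### Protocol 9.2.4 takes admissions booked after the first dose out of the SAE hospitalisation criterion, even for illness that began or worsened after vaccination, and SAP 4.1 words the rule differently

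*Protocol*

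**What the plan says.** Protocol section 9.2.4 treats an adverse event as serious if "in the view of either the investigator or sponsor, it results in any of the following outcomes/meets any of the following", followed by a list. The hospitalisation item carries an exception, "excluding pre-planned elective surgeries or other pre-planned hospitalizations", and the exception is then extended: "for this option it is not required that they were pre-planned solely before Visit 1, they might be pre-planned also after Visit 1".

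SAP section 4.1 defines the same item as "inpatient hospitalization or prolongation of existing hospitalization (excluding pre-planned elective surgeries or other pre-planned hospitalizations". The exception is there, but the extension to planning after Visit 1 is not. SAP section 11, which lists departures from the protocol, does not mention the difference.

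Protocol section 3.2.1 names five primary safety outcomes. Two rest on the SAE definition: vaccine-related SAEs, and "Occurrence of all SAEs, regardless of the assessment of relatedness". The other three are NOCIs, solicited reactions, and unsolicited AEs through 22 days after each vaccination.

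Section 9.2.1 adds two recording rules. Unsolicited events that are not SAEs, ILI, AESIs or NOCIs stay out of the AE section of the eCRF once they fall beyond about 22 days after vaccination, though they must still be noted in the site's subject file. And "if the severity of any pre-existing medical condition increases, it may be recorded as an AE or SAE".

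**The concern.** Visit 1 is Day 0, when the first dose is given (Protocol 7.1). An exception for admissions arranged before that day removes events that the vaccine cannot have caused. Once the arranging may also happen after Visit 1, that logic no longer holds, and the text puts no other limit in its place. It does not ask that the condition existed before dosing or that it stayed stable. Nor does it say how far ahead an admission must be booked to count as pre-planned.

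The same post-vaccination illness is then serious if the subject is admitted that day, and not serious by this criterion if the subject is given an appointment. SAE status also drives reporting within 24 hours and DSMB review (Protocol 9.2.4 and 9.3.1), so more than a table entry depends on it.

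**Working it through.** There is no figure in the plan to reproduce. The question is one of definition, so the check traces what happens to an admission booked after Visit 1.

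1. **Does the exception reach new or worsened illness?** Yes. The SAE list applies only to events that are AEs. Under Protocol 9.2.1 a condition present at screening is baseline and is not reported as an AE unless it worsens. An unchanged pre-existing condition is therefore largely outside the SAE definition already. The events whose status the post-Visit-1 extension chiefly changes are those that are AEs, that is, illness that began or worsened.

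2. **Is the event lost altogether?** That depends on its type:
   - *Chronic illness that began or worsened after vaccination.* Not an SAE by hospitalisation, but still a NOCI (9.2.1). NOCIs are a primary safety outcome and are documented throughout participation (9.3). If the booked admission was its only serious feature, it drops out of the serious-NOCI row of the SAP's general AE summary (SAP 4.4).
   - *Non-chronic illness starting within 22 days of a dose.* Not an SAE by hospitalisation, but still an unsolicited AE and so still in a primary safety outcome, as a non-serious event.
   - *An AESI, or an event meeting another criterion.* Still an SAE. The protocol says "all AESIs will also be considered SAEs", and death, threat to life, incapacity, congenital anomaly and important medical event are untouched.
   - *Non-chronic illness starting outside the 22-day windows and meeting no other criterion.* Reaches no primary safety outcome. Unless it is an ILI, which is recorded on its own track, it is also kept out of the AE section of the eCRF. Visit 4 asks only about NOCIs and SAEs (7.4).

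3. **Can the SAP recover the last group?** No. SAP 4.4 plans further tables of all unsolicited AEs up to 30 days after Visit 4, but they can show only what was entered in the database.

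4. **Do the two documents agree?** No. Sites record under Protocol 9.2.4, and the SAP tabulates those records under a definition without the extension. Someone reading the SAP would assume a narrower exception than the one sites were given.

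5. **Was the rule the same for both cohorts?** Possibly not. The protocol's summary of changes, used here only for timing, places the extension in version 4.0, dated 27 March 2019. Cohort 1 (4,055 subjects) finished at the latest on 15 May of that season (7.5). Cohort 2 (about 8,000) falls wholly under the extension. SAP 4.4 pools SAEs over both seasons and also shows them by season. When sites began to apply the clause is not stated.

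**The case against.** The best defence is that the exception sits inside one item of a list in which any item suffices. The important-medical-event item applies where "based upon appropriate medical judgment they may jeopardize the patient or subject", does not require admission, and can be invoked by investigator or sponsor. Together with the NOCI and 22-day AE outcomes, it leaves a narrow gap. Late non-serious events remain in site files, and the DSMB may ask for more data (9.5). The clause may also have been meant only for routine procedures on stable conditions.

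Most of this stands and limits the point. It does not close the gap. The important-medical-event route is discretionary, the protocol gives no test for what counts as chronic, and the text does not confine the clause to stable conditions.

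A reader might infer three stronger things that the documents do not support:
- *That all such admissions leave primary safety.* Only the last group in step 2 does.
- *That slowly developing illness is selectively removed.* Much of it would be chronic, and the NOCI outcome exists to count it.
- *That an arm comparison is biased or loses a known amount of precision.* Investigators and assessors are blinded (5.3.2), so undercounting is expected in both arms. For SAEs the plan has listings, counts by group and within-group exact intervals (Protocol 11.5.2, SAP 4.4), and no between-arm SAE ratio.

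**Conclusion.** The point holds in limited form. As written, Protocol 9.2.4 makes seriousness by hospitalisation depend on how an admission was arranged, including for illness that began or worsened after the first dose. All SAEs and vaccine-related SAEs are understated in both arms to whatever extent such admissions occur and meet no other criterion. Complete loss from the primary safety outcomes is confined to non-chronic illness starting outside the 22-day windows that meets no other criterion. Protocol 9.2.4 and SAP 4.1 do not match.

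The size cannot be derived. The documents give no hospitalisation rate and no share of booked admissions, and say only that few SAEs are expected (Protocol 11.5.2). Any count would rest entirely on assumed inputs. No direction of bias between arms is shown, and the efficacy analysis is unaffected. This should be corrected because it concerns a stated primary safety outcome and is cheap to repair, but it does not undermine the trial.

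**What to change.** - **Protocol 9.2.4:** limit the exception to admissions planned before the first vaccination for a condition that did not begin or worsen afterwards. By step 1, this should not bring in routine procedures on unchanged baseline conditions, because those are not AEs.
- **Protocol 9.2.1:** for worsened pre-existing conditions, replace *may* with *will* be recorded, within the existing recording windows.
- **SAP 4.1:** carry the same wording on both points, and list in SAP section 11 any difference that remains.
- **Before unblinding:** ask sites in both cohorts for admissions not reported as SAEs because they were planned after Visit 1. The site files should hold many of them. Classify these blind and document the result with the blinded data review.

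The cost is two sentences of protocol text with matching SAP and eCRF guidance, a modest amount of site query work, and a slightly higher reported SAE rate in both arms.

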9.3. Reporting Procedures

Solicited injection site and systemic reactogenicity events will be documented from the time of each study vaccination (Day 0 (Visit 1) and approximately Day 22 (Visit 2) through 8 days after each study vaccination (day of the vaccination inclusive).

Unsolicited non-serious AEs (excluding NOCIs) will be documented from the time of the study vaccination until 22 days after the study vaccination (day of the vaccination inclusive).

ILI will be documented as AE if occurs within 8 days post vaccination (day of the vaccination inclusive).

SAEs and NOCIs will be documented from the time of the first study vaccination (Day 0 (Visit 1)) through subject’s participation in the trial.

SAEs occurring after the participant completes the study or after early termination need not be reported unless the Investigator believes that the event may have been caused by the study product or a protocol procedure.

